## INTRODUCTION

Total hip replacement is a commonly performed surgical procedure with up to 4,500 procedures performed annually in Ireland and up to 400,000 per year in the United States. Most of the patients experience moderate to severe pain in the initial post-operative period. Multimodal analgesia with peripheral nerve blockade is recommended as gold standard for management of lower limb joint replacements. The limitations with peripheral nerve blocks include limited duration of effect with single shot injections and associated motor block which can delay rehabilitation.

Transmuscular Quadratus lumborum (TQL) block has been described recently as an effective option for post-operative analgesia in patients undergoing total hip replacements with single injection providing analgesia for up to 24 hours. We hypothesise that a single injection TQL block when compared to single injection fascia iliaca block (FIB) will provide better analgesia and less motor block in the initial 24 hour period.

## METHODS

This prospective, randomised controlled trial will be conducted in patients undergoing total hip replacement surgeries under spinal anaesthesia. Ethical committee approval has been obtained from the Research Ethics Committee (REC) in Tallaght hospital and the study will be registered in Clinicaltrials.gov database. All patients scheduled for elective total hip replacement surgery will be contacted up to 24 hours prior to the surgery by telephone. Information about the nature and purpose of the study will be provided to them by Anaesthetic trainees who are part of the study team. Informed written consent will be obtained from all consenting patients prior to participation in the study.

Randomisation will be carried out by computer generated random numbers and allocation will be enclosed in sealed envelopes. Patients and Outcome assessors will be blinded to the study group. The following are the inclusion and exclusion criteria.

### ***Inclusion Criteria***

Patients undergoing elective total hip replacements under spinal anaesthesia

ASA 1-3

Age > 18 yrs.

Written informed consent

***Exclusion Criteria***

Local infection

Allergy to local anaesthetics

Severe coagulopathy

***Primary Outcome Measure:***

24 hour morphine consumption between the two groups

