### **Fascia Iliaca Block (FIB):**

Following the administration of spinal anaesthetic, the patient will be positioned supine. Skin decontamination of the block site will be done with 2% Chlorhexidine (Chloraprep 3 ml applicator, CareFusion Corporation, San Diego, CA 92130, USA). Under strict aseptic precautions (cap, mask, sterile gloves, sterile probe cover and sterile ultrasound gel), a 80 mm (Stimuplex® Ultra 360® 22 gauge insulated echogenic needle with 30° bevel and extension set) needle will be used to perform FIB. A linear high frequency probe (8-13 MHz) will be placed along the inguinal crease to identify the femoral artery, femoral nerve and Iliacus fascia. The needle will be advanced by in-plane technique and local anaesthetic will be deposited under the fascial iliaca. 20 ml of 0.25% bupivacaine will be administered under USG guidance following careful intermittent aspiration.

All patients (unless contraindicated) will receive intra-operative intravenous medication viz: paracetamol 1gm, Parecoxib 40mg, tranexamic acid 1gm and antibiotics as per local guidelines. Perioperative sedation will be left to the discretion of the anaesthetist.

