### **Postoperatively:**

Following transfer to recovery unit, if patient reports pain score by numerical rating score >3, morphine 2 mg increments will be given intravenously by the recovery staff. This will be repeated every 5 minutes till the pain score is <4. In patients needing more than 10 mg of morphine in the recovery, anaesthetist will be requested to review the patient. Post-operatively, in the absence of contraindications, all patients will be prescribed regular paracetamol 1g every 6 hourly and celecoxib 200 mg, 12 hourly. Anti-emetics (ondansetron 4 mg, 8 hourly and Cyclizine 50 mg, 8 hourly) will be prescribed for all patients to be administered as required. All patients will receive morphine PCA in post-operative period. All patients will be reviewed at 6 hours and 24 hours to assess the pain scores and motor block.

Statistics:

A sample size of 46 patients (23 per group) is estimated based on 50% reduction in morphine consumption with power of 80% and alfa error of 0.05%. To allow for the drop outs, we aim to recruit 50 patients in total.

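### Does the primary outcome need a stated start time, a list of morphine sources and a rule for other opioids?

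*Protocol*

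**What the plan says.** The Primary Outcome Measure section consists of one phrase: "24 hour morphine consumption between the two groups". The Introduction's hypothesis is that the quadratus lumborum block "will provide better analgesia and less motor block in the initial 24 hour period", again with no event that starts the clock.

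The Postoperatively section gives morphine by two routes. In recovery, for a pain score above 3, "morphine 2 mg increments will be given intravenously by the recovery staff", repeated every 5 minutes until the score is below 4. Then "All patients will receive morphine PCA in post-operative period". If recovery use is high, "In patients needing more than 10 mg of morphine in the recovery, anaesthetist will be requested to review the patient"; what happens after that review is not described. The follow-up visits are also given without an origin: "All patients will be reviewed at 6 hours and 24 hours to assess the pain scores and motor block".

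Two other statements bear on the point. The Fascia Iliaca Block section ends with "Perioperative sedation will be left to the discretion of the anaesthetist", and Methods states that "Patients and Outcome assessors will be blinded to the study group".

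**The concern.** A primary outcome should be one that two people, given the same records, would compute identically. Here at least three start points fit the words: block injection, arrival in recovery and start of PCA. The last would leave out the recovery boluses, which can reach 10 mg before a review is requested. The choice could alter the size of the effect and the power, and it could be made after the data are seen. The sample size rests on a 50% reduction in morphine consumption, so one would also want to know which total that 50% describes.

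The second worry is that the outcome counts morphine alone. Sedation is discretionary, treatment after the recovery review is open, and the anaesthetist is not listed among those blinded. If another opioid were given, the outcome would miss it. Rescue of that kind would tend to fall in the arm with more pain, which would pull the estimated difference towards zero.

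**Working it through.** **The plan's own figure.** The protocol gives 23 per group, 80% power and a 50% reduction, but no control mean or SD. Taking alpha as 0.05 two-sided (an assumption; the document prints 0.05%), the detectable standardised difference by the normal approximation is (1.960 + 0.842) × √(2/23) = 0.826. The SD must then be 0.5/0.826 = 0.605 of the control mean. The sample size can be neither confirmed nor refuted, and the sizes below all rest on assumed inputs.

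**Leaving recovery morphine out, when the total falls by 50%.** Let s be recovery's share of control-arm morphine and r the reduction in recovery morphine. The reduction in the remainder is x = (0.50 − s·r)/(1 − s).

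| s | r | x |
|---|---|---|
| 0.20 | 0 | 0.50/0.80 = 62.5% |
| 0.20 | 0.50 | 0.40/0.80 = 50% |
| 0.20 | 0.75 | 0.35/0.80 = 43.75% |
| 0.10 | 0 | 0.50/0.90 = 55.6% |
| 0.10 | 0.75 | 0.425/0.90 = 47.2% |

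The shift can go either way, and it vanishes if recovery use falls in the same proportion as the rest.

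**Counting recovery morphine, when later morphine falls by 50%.** Assume a later control mean M with SD 0.6M, recovery mean R equal in both arms with SD R, and independence of the two. The reduction is 0.5M/(M + R). Power is Φ(0.5M/√((0.6M)² + R²) × √(23/2) − 1.96).

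- Recovery left out: 50%, power about 81%.
- M = 30 mg, R = 2 mg: 15/32 = 47%, power 80%.
- M = 20 mg, R = 5 mg: 10/25 = 40%, power 74%.
- M = 10 mg, R = 10 mg: 5/20 = 25%, power 31%. In this corner recovery supplies half of all control-arm morphine.

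These figures show what would happen if the two totals were treated as interchangeable. They do not show that the protocol leaves the two readings equally open.

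**Which reading the text supports.** The outcome names the drug, not the delivery device. The recovery boluses are morphine, directed by the protocol and given after surgery. The Postoperatively section opens with transfer to recovery and then covers boluses, PCA and both reviews. That order points to a postoperative clock with everything in it. Block injection and recovery arrival differ as start points, but the protocol directs no morphine between them, so both windows hold the boluses. They part only in the last hours of PCA use. If surgery and transfer take h hours and hourly use is roughly steady within each arm, both arms lose the same fraction h/24 and the relative reduction does not move.

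**Other opioids.** The spinal is plain bupivacaine, both blocks are bupivacaine, the listed intra-operative drugs are paracetamol, parecoxib, tranexamic acid and antibiotics, and postoperative opioid is morphine in recovery and by PCA. No other opioid appears.

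**If rescue did go uncounted.** Take log-normal consumption with coefficient of variation 0.592 (0.5/0.845, where 0.845 is the detectable difference from the t-test calculation) and a true reduction of 50%. Let patients above the control arm's 80th centile have the excess over that centile cut by a quarter, a half or three quarters. The observed reduction is 48.7%, 47.4% or 45.9%. Simulated power with 23 per group is 97.2% with no cut and 97.6%, 98.0% and 98.2% with the cuts. Trimming the upper tail reduces variance enough to offset the smaller difference.

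This model is rough. Its trigger is a centile of the 24-hour total, not the 10 mg in recovery that the protocol uses. Its power starts above 80% chiefly because a common coefficient of variation halves the treated arm's SD. It serves only to show that the effect is small.

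**The case for a change.** The best case for a change is that the content and time frame of a primary outcome belong in the protocol, because they decide what staff record. A later analysis plan cannot recover a block time or a dose that nobody wrote down. The wording would be cheap to add, and a PCA-only total is a reading that someone could adopt.

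Part of this stands. The start time and the list of sources are indeed unwritten, and stating them would do no harm. The rest carries less weight. Nothing in the protocol suggests that the boluses or PCA doses would go unrecorded: recovery staff give the first in counted 2 mg steps, and the review threshold requires a running total. The PCA-only reading has to narrow the outcome's own words. The argument about other opioids depends on drugs the document never mentions. The blinding statement concerns who knows the allocation, not what is counted. Converting everything to morphine equivalents would alter the endpoint and bring in approximate conversion factors, for a gain the document gives no reason to expect.

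**Conclusion.** No change is called for. The missing start time and component list are a gap in detail, which analysts would fill by summing recovery boluses and PCA over the first 24 postoperative hours, or which an analysis plan not shown here may already settle. The gap applies equally to both arms and creates no bias between them. Following the protocol as written would not give a wrong result.

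The larger shifts, from 50% to 44% or 62.5%, or down to 25% with power of 31%, require assumed recovery shares and a choice between readings that the text does not leave evenly balanced. The direction also depends on the assumptions. If residual spinal anaesthesia does make the arms alike in recovery, few patients there would need morphine and the share at issue would be small. The other-opioid point rests on conjecture and, on its own model, moves the estimate by about 1 to 4 percentage points without costing power. The conclusion assumes that morphine is the only opioid used, as the protocol describes, and that recovery doses are recorded.

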***Secondary outcome***

Motor block assessed by the Modified Bromage Scale

Numerical Rating Scale (NRS) score for pain

***Detailed description***

Consenting patients will be randomised to undergo either Transmuscular Quadratus Lumborum block (TQL) or Fascia Iliaca Block (FIB).

On arrival to the anesthesia induction room baseline monitoring (non-invasive blood pressure, pulse oximetry and 3 lead ECG) and intravenous access will be established. Patients in both groups will then be positioned sitting on a level trolley with feet resting on a foot rest. They will be given a pillow to hug and requested to maintain an arched back posture with an assistant holding the patient to aid positioning. No sedation will be given prior to or during administration of spinal anesthesia.

Spinal anaesthesia will be performed under strict aseptic precautions (Chlorhexidine 0.5% for skin decontamination with anaesthetist performing the procedure scrubbed wearing sterile gown, cap and sterile gloves). 25G Whitacre needle will be used and 3.2ml 0.5% plain bupivacaine will be administered.

***Transmuscular Quadratus Lumborum Block (TQL):***

Following the administration of spinal anaesthetic, the patient will be positioned laterally with the operating side as the non dependant side. Skin decontamination of the block site will be done with 2% Chlorhexidine (Chloraprep 3 ml applicator, CareFusion Corporation, San Diego, CA 92130, USA). Under strict aseptic precautions (cap, mask, sterile gloves, sterile probe cover

and sterile ultrasound gel), a 100 mm (Stimuplex® Ultra 360® 22 gauge insulated echogenic needle with 30° bevel and extension set) needle will be used to perform TQL block. A curvilinear low frequency probe (2-5 MHz) will be placed above the iliac crest and the following structures will be identified i) Transverse process ii) Erector spinae muscle iii) Quadratus lumborum muscle iv) Psoas major muscle. The needle will be advanced by in-plane technique and local anaesthetic will be deposited between psoas major and quadratus lumborum muscles. 20 ml of 0.25% bupivacaine will be administered under USG guidance following careful intermittent aspiration.

### **Fascia Iliaca Block (FIB):**

Following the administration of spinal anaesthetic, the patient will be positioned supine. Skin decontamination of the block site will be done with 2% Chlorhexidine (Chloraprep 3 ml applicator, CareFusion Corporation, San Diego, CA 92130, USA). Under strict aseptic precautions (cap, mask, sterile gloves, sterile probe cover and sterile ultrasound gel), a 80 mm (Stimuplex® Ultra 360® 22 gauge insulated echogenic needle with 30° bevel and extension set) needle will be used to perform FIB. A linear high frequency probe (8-13 MHz) will be placed along the inguinal crease to identify the femoral artery, femoral nerve and Iliacus fascia. The needle will be advanced by in-plane technique and local anaesthetic will be deposited under the fascial iliaca. 20 ml of 0.25% bupivacaine will be administered under USG guidance following careful intermittent aspiration.

All patients (unless contraindicated) will receive intra-operative intravenous medication viz: paracetamol 1gm, Parecoxib 40mg, tranexamic acid 1gm and antibiotics as per local guidelines. Perioperative sedation will be left to the discretion of the anaesthetist.

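### Sedation is left to an anaesthetist not listed as blinded, with no limit on agent; analgesic sedatives, if used unequally by arm, could bias the 24-hour morphine comparison

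*Protocol*

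**What the plan says.** The sedation rule is the last sentence of the Protocol section Fascia Iliaca Block (FIB): "Perioperative sedation will be left to the discretion of the anaesthetist". Although it stands under the FIB heading, it closes a paragraph about intra-operative drugs for all patients, so it is read here as applying to both arms. The only other rule on sedation, in the Detailed description, limits timing: "No sedation will be given prior to or during administration of spinal anesthesia".

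On blinding, METHODS states: "Patients and Outcome assessors will be blinded to the study group". The anaesthetist is not listed. The arms differ in plain view once the spinal is in. For the quadratus lumborum (TQL) block, "the patient will be positioned laterally with the operating side as the non dependant side". For FIB, "Following the administration of spinal anaesthetic, the patient will be positioned supine". The probe and injection site differ too.

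The primary outcome is "24 hour morphine consumption between the two groups". Under Postoperatively, a recovery pain score above 3 triggers treatment, in which "morphine 2 mg increments will be given intravenously by the recovery staff"; all patients also have morphine PCA.

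**The concern.** The protocol fixes nearly every other analgesic input: the spinal dose, the block drug and volume, intra-operative paracetamol and parecoxib, the recovery morphine rule, regular paracetamol and celecoxib, and PCA. Sedation is the route left open. A sedative with analgesic effect would be given before the recovery pain score and before PCA, so it could reduce the morphine that is counted. The protocol does not say that such a drug is recorded for the trial or counted.

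Randomisation does not protect against a treatment choice made after the arm is known, and no part of the text blinds the person making this choice. If the choice differed by arm, part of the observed difference in morphine would reflect sedation and not the block. Depending on direction, that could create a false difference, hide a real one or overstate one.

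**Working it through.** **Step 1: what the text allows.** The FIB section gives discretion without naming an agent. The Detailed description bars sedation only up to the end of the spinal. Together they permit any sedative after the spinal, including one given after the block, when anyone who was present knows the arm. No sentence excludes an opioid, ketamine or an alpha-2 agonist.

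**Step 2: who chooses.** The Detailed description has the spinal given "with anaesthetist performing the procedure scrubbed wearing sterile gown, cap and sterile gloves", directly before the block. The text does not say whether that person also chooses the sedation.

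**Step 3: inputs for size.** From Postoperatively (Statistics): 23 per group, a 50% reduction, 80% power. The alpha is printed as 0.05%; it is read here as 0.05 two-sided, which is an assumption. No mean or SD is given, so the stated sample size cannot be reproduced forwards. It can only be solved backwards for the SD it implies.

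For a two-sample t-test (noncentral t) with 23 per group and 80% power, the standardised difference is d = 0.845. Hence SD = 0.5 × mean / 0.845. Two comparator means are assumed:

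- 20 mg: target difference 10 mg, SD = 10 / 0.845 = 11.8 mg.
- 40 mg: target difference 20 mg, SD = 20 / 0.845 = 23.7 mg.

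**Step 4: assumed shifts.** Net shift in one arm's mean = excess share of patients given an analgesic sedative × mg of morphine replaced per user:

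- 0.1 × 5 = 0.5 mg
- 0.1 × 10 = 0.2 × 5 = 1 mg
- 0.2 × 10 = 2 mg

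For scale, 2 mg is one recovery increment averaged over every patient in an arm.

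**Step 5: results.** The false-positive rate is the rejection rate at d = shift / SD. Power against an opposing shift is taken at d = (target − shift) / SD. For example, at a mean of 20 mg and a shift of 2 mg, these are 2 / 11.8 = 0.169 and (10 − 2) / 11.8 = 0.676.

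| Comparator mean | Shift | Share of target | False-positive rate | Power, opposing shift |
|---|---|---|---|---|
| 20 mg | 0.5 mg | 5% | 5.2% | 75.9% |
| 20 mg | 1 mg | 10% | 5.9% | 71.3% |
| 20 mg | 2 mg | 20% | 8.7% | 61.1% |
| 40 mg | 0.5 mg | 2.5% | 5.1% | 78.0% |
| 40 mg | 1 mg | 5% | 5.2% | 75.9% |
| 40 mg | 2 mg | 10% | 5.9% | 71.3% |

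If the shift runs with the true effect, the difference is overstated by the same 0.5 to 2 mg. With no analgesic sedative, or with equal use, the bias is nil. No power loss from added noise is claimed, because the unstated planning SD may already include variation in sedation.

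**The case against.** The strongest reply is that nothing here is an error or a contradiction. Discretionary sedation under a spinal is a stated choice that applies to both arms, and reading sedation as licence for opioid analgesia is possible but not the natural reading. Bias needs three things together: an analgesic agent, an effect lasting into recovery or PCA, and unequal use. The text gives little reason to expect the third. Both arms have the same spinal, block volume and concentration, and the same paracetamol and parecoxib. Knowing the arm is not in itself a motive to sedate differently. Patients and assessors are blinded, recovery morphine follows a pain-score rule, and PCA is in the patient's hands.

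Most of this stands. It limits the likelihood and the size, but does not close the route: the text permits such agents, and does not blind whoever chooses them.

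It can also be said that 50 patients are to be recruited. With 25 per group the mean-40 powers become 81.4%, 79.4% and 75.0%. That improves power but leaves the shift itself unchanged.

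A reader might infer that the anaesthetist who performs the block will sedate the two arms differently, or that discretionary sedation by itself biases the primary outcome. The documents support neither. They do not identify who sedates, report no pattern of sedative use and do not suggest that the arms would differ in need. Finally, how intra-operative opioid is counted may be covered in an SAP that is not at hand; but the choice of drugs in theatre is trial conduct, which the protocol has to set.

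**Conclusion.** The point holds in a conditional form. The sedation rule allows agents that act on the primary outcome, chosen by someone not listed as blinded, and unequal use by arm could bias the morphine comparison. Unequal use is a possibility the text leaves open, not something it shows.

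The illustrated effect is mostly small. Only one of the six cases is material (8.7% and 61.1%), and it needs a 20-point excess in use, 10 mg replaced per user and a 20 mg comparator mean all at once. Ten milligrams would be half of that assumed 24-hour mean. The means, the excess use, the milligrams replaced and the reading of alpha are all assumptions, and the direction of any bias is unknown. This is an optional, inexpensive tightening of the protocol; confidence that it matters in practice is at most medium.

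**What to change.** Replace the sedation sentence with:

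*Perioperative sedation, if used, will be with non-analgesic agents only in both groups. Any opioid, ketamine or alpha-2 agonist given intra-operatively for clinical need will be recorded with dose and reason; intra-operative opioid will be added to the 24-hour total as intravenous morphine equivalents in a sensitivity analysis, and use of these agents will be reported by group.*

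The exception for clinical need leaves some choice with the same anaesthetist, so the rule reduces the exposure without removing it. Recording and reporting by group let the reader see whether use was balanced. Ketamine and alpha-2 agonists are not converted to morphine; they are only reported.

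The cost is one protocol sentence, a small loss of anaesthetist discretion and a little extra recording in 50 patients. No added patients, visits or equipment are needed.
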